5.8. Randomisation Procedure

All subjects that meet the inclusion and exclusion criteria will be randomised to one of two treatment sequences. Both sequences examine the investigational product and the comparator investigational product. The two sequences are:

- First sequence: The investigational product, then the comparator investigational products.

- Second sequence: The comparator investigational product, then the investigational product.

Randomization will be centralized using [REDACTED]

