6.1. Inclusion criteria

To be included in the investigation a subject must comply with the following inclusion criteria:
1. Has given written consent to participate by signing the Informed Consent Signature Form
2. Be at least 18 years of age and have full legal capacity
3. Is able to handle (apply, remove, cut, etc.) the product and do the assessments themselves
4. Has an ileostomy or colostomy with consistent liquid fecal output (for colostomy: 6-7 Bristol stool scale*)
*See appendix 1
5. Currently use SenSura Mio Click 2p Click flat or concave with 50 mm coupling size
6. Have had their ostomy for at least 90 days
7. Be willing to change the bag at least twice per week
8. Is willing and suitable (determined by the Principal Investigator or designee) to use flat or concave 2p open product during the investigation
9. Is willing to use 2p maxi open bags during the investigation

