7.1. Subject Visits

Visit 0 - Screening (Day 0)

If a potential subject is interested in participating after the first contact, a visit (visit 0) will be arranged. When arranging the visit, it will be ensured, that the subject has received the Subject Information Form and given

plenty of time to review it. The subject will receive both written and verbal information to ensure that the subject understands what was read and explained and can freely agree to participate in the investigation. The subject will, beforehand, also be informed about the possibility of bringing a companion to any subsequent visits. During the visit, the Principal Investigator or designee will provide oral information about the investigation based on the Subject Information Form. The subject has the right to wait before deciding on participation.

Visit 1 – Inclusion (Day 1)

If/when subjects decide to participate, they will be asked to sign the Informed Consent Signature Form. If a subject so desires, and it is certain that it is understood what the investigation entails, and the informed consent form has been signed, the subject is considered enrolled in the investigation. Enrolled subjects are entered in the electronic data capture system and will be randomised to either the test product or comparator. If a subject is enrolled and does not meet inclusion/exclusion criteria, they will be deemed screen failures and will not be randomized.

Once the subject has consented, the investigator and/or delegated site personnel will conduct the following:

- The investigator/study nurse will re-review study procedures.
- Subject is allocated a subject number
- Verification of inclusion/exclusion criteria
- Randomization (including subject number & name/type of randomized product)
- Collection of baseline data
 - Demographics (age, gender, height, and weight)
 - Current product (flat/concave, bag size, item numbers)
 - Stoma (age, type, cause, size, shape)
 - Bristol scale score (Appendix 1)
 - Output frequency
- Shipment of investigational products to subject

Visit 2 – Start of first test period (Day 3 + 2 days)

- Study Personnel will review App with subject and collect safety data, if applicable.
- First application of investigational product – test product OR comparator (Day 1 of Test period 1)

Test period 1:

- Testing test product / comparator product for 21 ± 2 days
- Telephone Visit at Day 7 ± 1 after application of product/comparator:

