 - Investigator/study nurse must call the subject to ensure that the subject is compliant with:
 - Study procedures and
 - Completion of subject diary
- Diary completion at every bag change
- Adverse Events, if applicable
- Device Deficiencies, if applicable
- Protocol Deviations, if applicable

Visit 3 - Cross-over Visit (Day 25 ± 2 days)

- Subject will be contacted by investigator/study nurse to review procedure for cross-over
- Study Personnel will review compliance with subject and collect safety data, if applicable. Application of investigational product - test product OR comparator (Day 1 of Test period 2)
- Adverse Events, if applicable
- Device Deficiencies, if applicable
- Protocol Deviations, if applicable

Test period 2:

- Testing test product / comparator product for 21 ± 2 days
- Telephone Visit at Day 7 ± 1 after application of product/comparator:
 - Investigator/study nurse must call the subject to ensure that the subject is compliant with:
 - Study procedures and
 - Completion of subject diary
- Diary completion at every bag change
- Adverse Events, if applicable
- Device Deficiencies, if applicable
- Protocol Deviations, if applicable

Visit 4 – Completion/Termination (Day 46 ± 2 days)

- Subject will be contacted by investigator/study nurse for study completion or termination
- Study Personnel will review compliance with subject and collect safety data, if applicable.

NOTE:

1. See Appendix 2 for details on the subject questions included in the subject diary. The subject diary will be provided to the subjects using an app installed on their smart phones.
2. Subjects who are unable to complete a test period may move forward to the next visit and test period instead of dropping out of the investigation.

7.2. Safety Follow up:

Adverse events and device deficiencies will be assessed at all visits, planned and unplanned. Subjects are followed through termination of the investigation (Visit 4). Any ongoing ADEs or SADEs at study termination will be followed until resolution. All subjects are encouraged to contact the Principal Investigator, or designee, if they experience problems that they believe are related to their investigational product or participation. This is to ensure that any device-related events are documented and to safeguard the subjects' health.

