7.3. Schedule of Assessments

Table 1- Study assessments.

	PERFORMED BY	VISIT 1	VISIT 2	VISIT 3	VISIT 4
Informed consent (Allocation of Subject Number in EDC)	Investigator/Delegated Site Personnel	X			
Inclusion/Exclusion criteria	Investigator/Delegated Site Personnel	X			
Shipment of investigational products	Investigator/Delegated Site Personnel	X			
Randomization	Investigator/Delegated Site Personnel	X			
Baseline Data Collected	Investigator/Delegated Site Personnel	X			
Application of device (test product or comparator)	Subject		X	X	
Questionnaire completed at each bag change during test period 1 & 2	Subject		X	X	
Final evaluation questionnaire completed at end of study					X
Ensure Compliance	Investigator/Delegated Site Personnel		X	X	X
Telephone Call	Investigator/Delegated Site Personnel		(Day 7 of test period 1)	(Day 7 of test period 2)	
Protocol Deviations, If applicable	Investigator/Delegated Site Personnel	X	X	X	X
Adverse Events, if applicable	Investigator/Delegated Site Personnel	X	X	X	X
Device Deficiency, if applicable	Investigator/Delegated Site Personnel		X	X	X

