This Patient Cloud app is used during the investigation every time the subject makes a bag (2pc) change.

The ePRO used is [REDACTED] All data will be transferred automatically into the eCRF. If for some reason the app is not available before FPI the patient reported outcome questionnaires will be reported by using a paper diary which will be handed out to all subjects.

In the unforeseen situation, where site cannot establish connection to the EDC system a paper CRF (pCRF) has been printed and supplied by sponsor.

The investigator will keep a separate list of the subjects' ID numbers, names and addresses in a locked room/cabinet. Only data referred to in this clinical investigation plan will be recorded in the CRFs.

Database Management, Queries and Quality Control

The data management system has restricted role-based access control. The principal investigator or delegate must be trained in the system prior to getting access. The training is web-based and must be completed before access to the investigation is granted. Training will be documented in the data management system. Only the principal investigator, or delegate, will be authorised to enter data in the eCRF.

The monitor, using his/her personal login information shall verify all critical data points against the source documents and issue electronic queries for the authorised clinical site personnel to respond, as defined in the monitoring plan.

The principal investigator, using his/her personal login information shall sign each eCRF.

Automated, real time access to the data enable control on study compliance and safety assessments.

A critical quality control will be performed by the sponsor's data management team and queries issued where needed. Such queries will be reviewed by the monitor and must be resolved by the site personnel.

At the end of the study a formal data review meeting will be performed before the database will be locked.

A full audit trail ensures, that each user's (site personnel, monitor, sponsor, data manager) access to and actions in the system is tracked.

The Data Management Procedures are further described in the Data Management SOPs.

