Appendix 2 – Instructions & Subject Questionnaire

The participants must be instructed in the following:

- Bag change frequency: Bags must be changed at least twice per week. Baseplates can be changed at bag change or left until next change as they choose. They are welcome to change more than twice per week. If baseplate is changed, the bag should also be changed.
- It is very important to explain to the participants what is meant by "feces having leaked out *through* the coupling" not to be confused with leakage from under baseplate that has spread to the coupling from the outside.
- Explain how to scrutinize the coupling before changing the bag. Look at it from all sides (with help of a mirror and/or smartphone where not visible to the eye). Drawings will be helpful for explaining what to look for.
- Be careful to instruct that at bag change, the coupling on the baseplate must be cleaned thoroughly so leakage of feces during wear time is not confused with feces not having been cleaned from the coupling at bag change.
- Make sure to check that the coupling is clean after bag change.
- If both bag and baseplate are changed at the same time, it is ok to take them off together as we do not ask questions related to opening of the coupling.
- Make sure participants are guided on remembering in which test period (1 or 2) they tested the new coupling when the final questions are asked at visit 3.

Overall procedure at every bag change:

- Look at the coupling from all angles before changing any of the products
- Change the bag (or bag and baseplate)
- If only a bag change is performed - remember to check that the coupling is clean after the change
- Register date and time in the app.
- Answer the questions in the app.

Questionnaire at each bag change:

- Are there any signs of feces having leaked through the coupling since last bag change? (yes/no), IF YES: How much leakage through the coupling has there been? Please choose one of the options below:

1. Small
2. Medium
3. Large

Note: Subjects will be provided with examples as reference. (Refer to appendix 3)

- Did you use any supporting accessories (yes/no) If yes, click for options (multiple choice):

1. Paste
2. Elastic barrier strips
3. Protective film
4. Deodorant
5. Adhesive remover
6. Cleanser for the skin
7. Tape around the outer edge of the adhesive
8. Moldable rings/seals
9. Belt
10. Powder
11. Skin care lotion
12. Hernia belt
13. Supporting garment
14. Other, please specify _____

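### Could the leakage answer given at the cross-over change be counted for the wrong product?

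*Combined protocol and SAP*

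**What the plan says.** The primary endpoint is a yes/no answer at each bag change. Appendix 2 tells the subject to inspect the coupling first, then change the bag, then record date and time in the app and answer: "Are there any signs of feces having leaked through the coupling since last bag change". The diary also asks about accessories and baseplate change. It has no visible item naming the product worn.

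Section 7.1 starts each period at an application. Visit 2 is "test product OR comparator (Day 1 of Test period 1") and Visit 3 is "test product OR comparator (Day 1 of Test period 2"). Diary completion is listed under the two test-period headings, not under the visits. Table 1 in section 7.3 has a row "Questionnaire completed at each bag change during test period 1 & 2", marked in the Visit 2 and Visit 3 columns, and a row "Final evaluation questionnaire completed at end of study", marked at Visit 4. Section 11.0 adds: "This Patient Cloud app is used during the investigation every time the subject makes a bag (2pc) change".

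Product follows from sequence and period under section 5.8, for example "Second sequence: The comparator investigational product, then the investigational product". Before the study, subjects wear the comparator coupling (section 6.1: "Currently use SenSura Mio Click 2p Click flat or concave with 50 mm coupling size"). Section 10.0 summarises endpoints by product and fits a logistic model with fixed product and period effects. Section 5.0 lets a subject who cannot complete a period with the test product use their own product for the rest of it, and requires the investigator to document this.

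**The concern.** The question looks back and the schedule looks forward. No washout is described, so a single bag change ends the first product and opens test period 2. An analyst who derived product mechanically from sequence and scheduled period would credit that answer to the wrong coupling in both sequences. If an answer were also recorded at the first application, it would describe pre-study wear. If Table 1's columns meant single visits, the last bag of period 2 would have no scheduled answer. Entries made after a switch to the subject's own product raise a similar question, because no visible sentence says which product label they carry.

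Mixing the two couplings pulls the odds ratio toward 1. Section 10.3 treats a non-significant difference as fulfilling the purpose of the investigation, so an error in this direction would favour the new coupling. With few bag changes per period, one misplaced answer in each subject's second period is not negligible.

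**Working it through.** **The plan's own figures.** 40 completers with 20% drop-out: 40/(1 − 0.20) = 50 randomised, as stated in section 10.1. Two changes a week for three weeks: 2 × 3 = 6 answers per period, the basis given in section 5.0. Daily changing (section 4.7) gives about 21. The leakage rates behind the 40 are redacted.

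**Worst case for the cross-over answer.** Let m be the answers per period, pT and pC the leakage proportions, and d = pT − pC. Suppose every Visit 3 answer is filed under period 2, with sequences 1:1.
- Test label: ½·pT + ½·[(m − 1)pT + pC]/m = pT − d/(2m)
- Comparator label: ½·pC + ½·[(m − 1)pC + pT]/m = pC + d/(2m)
- Observed difference: d·(1 − 1/m)

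| m | Difference lost | Answers under wrong coupling (40 subjects) |
|---|---|---|
| 6 | 1/6 = 17% | 40 of 480 (8.3%) |
| 21 | 1/21 = 5% | 40 of 1,680 (2.4%) |

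If only a share f of subjects is misfiled, the loss is f/m. For f = 10% and m = 6 it is 0.10/6 = 1.7%; for f = 0 it is nil. The documents give no value for f.

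**Illustration with assumed rates of 10% and 20%, m = 6, f = 100%.** Test label 0.20 − 0.10/12 = 0.1917; comparator label 0.10 + 0.10/12 = 0.1083. The odds ratio falls from 2.25 to (0.1917/0.8083)/(0.1083/0.8917) = 1.95. Simulation of the planned model (40 subjects; assumed random-effect SDs 1.5 for subject and 0.75 for subject by product; 2,000 trials per cell) puts the chance of a non-significant result at 16% with correct filing and 27% with all cross-over answers misfiled. At m = 21 it is 1–2% either way.

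**Does the plan call for such filing?** Setting the provisions side by side:
- Section 10.0 analyses by product. The Appendix 2 question fixes the interval as the wear since the previous change. Together they assign each answer to the product removed.
- The cross-over entry can be found from its date and time and the date of the Visit 3 application. Section 14 requires logs with lot, dates of use and subject identification.
- Section 10.0 provides a formal data review before database lock, and documented omission of invalid data points.

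**Visit 2.** Section 7.1 lists only app review and first application there. An answer about pre-study wear is therefore not clearly scheduled. If one were recorded, it would cover no study product.

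**Visit 4.** In Table 1 the telephone row places Day 7 of period 1 in the Visit 2 column and Day 7 of period 2 in the Visit 3 column. Those columns therefore carry whole-period activities, and the questionnaire row names both periods. No gap for the last period-2 bag follows.

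**Own-product entries.** No switching rate is given. Assume 5, 10 or 20% of subjects switch at mid-period, with m = 6 and rates of 10% and 20%. Kept under the test label, these entries cost about half the switching share if switching is random (simulated 2.5, 5 and 9.5%), and 7, 12 and 22% if the leakiest subjects switch. Labelled by the coupling worn, or omitted, the loss is about 1% or less.

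**The case for a change.** The strongest argument for a change is that the time stamp does not settle the matter unaided. Appendix 2 has the subject register date and time after the new bag is on. A simple rule assigning entries on or after application to the new product would therefore misfile exactly the cross-over answer. No diary item names the product, and the only visible question linking product to time is asked once, at the end, by test period. The statistician is blinded until lock (section 5.9), the error favours a pass under section 10.3, and a sentence costs almost nothing.

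Much of this is factually right. The visible text has no explicit attribution rule, and the closed form is correct on its premise. But the premise is an analyst who disregards the wording of the endpoint. Attribution to the bag removed is the plain reading. Finding the cross-over entry needs a date, not the treatment code, so blinding is no obstacle.

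Section 11.0 does leave open whether an answer is entered at the first application. Counting such answers as study product would raise the worst-case loss to 1.5/m (25% at m = 6), but that adds a second unsupported assumption to the first.

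On switching, the visible text does permit more than one label. The nearest stated rule, in section 6.5 for subjects sent products in the wrong order, analyses by the sequence actually used. With the duty to document switches, that points toward actual use.

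**Conclusion.** No change to the plan is needed. The cross-over change does sit on the boundary between periods, and the visible text does not say in so many words where its answer belongs. This is a detail that analysts fill sensibly from the question's wording, the dates, the device logs and the pre-lock review. It is not an analysis error written into the plan. Attributed to the product removed, the answers carry no bias. The ceiling if every cross-over answer were misfiled is a 17% loss of the risk difference at the minimum of 6 changes and 5% at daily changes; the share misfiled is purely hypothetical. The points about Visit 2 and Visit 4 are not established by the schedule. The own-product point matters only if those entries are kept under the test label and switching is common, and the documents give no rate. All significance and odds-ratio figures rest on assumed leakage rates, and the simulated ones also on assumed random-effect SDs. Because parts of sections 10.0 and 10.1 are redacted, an attribution rule there cannot be excluded.

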Appendix 3 – Examples of Leakage at Coupling
